#### Recruitment strategy and expected dropout

Unlike most trials, we do not foresee any recruitment problems. In 2016, 8000 patients presented themselves during the weekend at the ED.

For each patient the study period is the time between presentation at the ED and discharge at either the ED or the GPC. This is a time span of only a few hours so the dropout rate will be negligible. Only when a patient leaves the site before consultation at the ED or GPC he or she is a dropout. This number of patients leaving the ED without being seen after triage (i.e. dropouts) is one of the safety indicators we will study. The number of these patients is currently less than five per weekend. We are able to measure this number using the triage reports through iCAREdata. Patients who leave without being seen before the triage-consultation will not be analysed.

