# Hypotheses and Research questions

#### Medical aspect

Our primary hypothesis: the extended triage intervention will lead to a substantial increase in the proportion of patients seen by the GP.

Without the intervention, all study patients can be divided in three categories: seen by ED, seen by GPC and left without being seen (after the triage). By adding the compliance of the patient to the allocation advice we get the following table:

	Patient goes to GPC	Patient goes to ED	Left without being seen
Advice GPC	Compliant patient GPC	Non-compliant patient GPC	Left without being seen type 1
Advice ED	Non-compliant patient ED	Compliant patient ED	Left without being seen type 2

Table 1: patient categories

The proportion of study patients seen at the GPC is a combination of patients compliant to a GPC advice and patients not compliant to an ED advice. The latter category will probably be small.

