#### Design of the clinical trial

#### A controlled longitudinal prospective intervention trial

To answer the above-mentioned research questions we need a longitudinal prospective intervention trial.

To allow definitive conclusions for our questions we need a control group. Historical controls will have too much confounding (not all data is available, the ED was organised in a different way, the GPC was unknown for many patients). Individually randomised controls are impossible from a practical point of view and because of contamination (patients will talk to each other and will not understand why some get a GPC advice and others not). Finally, randomisation by shift is not possible because they overlap in time. Therefore, randomisation is only possible by weekend. We will roll out one control weekend out of every four intervention weekends.

During a control weekend, all data registration and collection will be the same as during intervention weekends but we will not inform patients about their allocation advice. The emergency physician will see all patients deciding to stay at the ED, without influence of the triage advice. As in standard clinical care, patients will have the right to change their mind and go spontaneously to the GPC. Another difference is the communication to the patient: during intervention weekends, we will inform them about the intervention using leaflets and broadcasting in the waiting room of the ED. During control weekends, we will only inform about MTS-triage in general but no about the GPC. We will always mention the iCAREdata opting-out procedure.

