#### **Inclusion and Exclusion**

We will systematically include all patients presenting at the ED during the weekend (the GPC is only open during the weekend starting from Friday 7 pm until Monday 6 am). By presentation at the ED we mean the patient is registered by the receptionist of the ED as a patient. Patients who just pass the ED to enter the hospital or who go directly to a medical department (e.g. obstetrics) are thus not included. The availability of a Belgian citizen national insurance number is the only inclusion criterion. This number is necessary to send the data needed for this study to the iCAREdata database. For the vast majority of patients this number is available. It will not be available for patients who present for the first time at the hospital and forgot all official documents. For patients without a Belgian identity (foreign citizens without Belgian health insurance, people without a legal status and babies less than one week old) the number is never available. The EDs own software allows us to calculate the number of excluded patients.

Patients arriving at the ED by an ambulance with a doctor or nurse (in Dutch called MUG or PIT) is the only exclusion criterion (these patients have already passed through a sort of triage). We estimate an exclusion rate of 15 patients per weekend.

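### Patients enter at registration, but those who leave before triage are left out of every analysis and not counted by weekend type, although waiting-room information differs by arm

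*Combined protocol and SAP*

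**What the plan says.** Under Inclusion and Exclusion the protocol states: "We will systematically include all patients presenting at the ED during the weekend". It fixes the point of entry: "By presentation at the ED we mean the patient is registered by the receptionist of the ED as a patient". The Sample size section words the primary question for patients presenting at the ED, and the study period for each patient starts at presentation.

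The planned categories start later. Under Medical aspect, "all study patients can be divided in three categories: seen by ED, seen by GPC and left without being seen (after the triage". Table 1 has no place for a registered patient who leaves before triage, and Recruitment strategy and expected dropout removes that patient: "Patients who leave without being seen before the triage-consultation will not be analysed".

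The same section uses dropout in two senses. One sentence covers anyone who goes away before seeing a doctor at either service. The next narrows it: "This number of patients leaving the ED without being seen after triage (i.e. dropouts) is one of the safety indicators we will study". The source is then named: "We are able to measure this number using the triage reports through iCAREdata". Research question 5 asks whether the intervention affects how many patients leave unseen, and does not limit this to the time after triage.

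The Design section says that "during intervention weekends, we will inform them about the intervention using leaflets and broadcasting in the waiting room of the ED", while on control weekends nothing is said about the GPC.

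**The concern.** Being triaged is an event that follows assignment of the weekend. Restricting the analysis to triaged patients is harmless if leaving before triage, and where the leavers go, is alike in both arms. The different waiting-room information gives a reason why it might not be.

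Two questions are exposed. For question 1, a registered patient who reads about the GPC and walks there before triage is a patient presenting at the ED and seen by a GP, but is not counted. For question 5, a registered patient who goes home before triage has left unseen, but does not appear in the indicator, because there is no triage report. For a given set of leavers these effects compete: each one who reaches the GPC is not unseen, and each one who goes home does not add to GP contacts.

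**Working it through.** **Inputs from the documents.** 8000 weekend presentations in 2016 and 15 exclusions per weekend. Over 52 weekends, N = 8000/52 − 15 = 138.8 eligible patients per weekend (assuming the exclusions fall within the 8000). Post-triage leavers are given as fewer than five per weekend; I use 4 in each arm.

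**Assumed inputs.** The share p of triaged patients seen by a GP is 1% on control weekends and 5% to 20% on intervention weekends. The number L of pre-triage leavers, and the share f of them who reach the GPC, are not in the documents. There is no planned figure to reproduce.

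**Formulas, per weekend.**
- Proportion seen by a GP among all registered eligible patients = ((N − L)·p + L·f)/N
- Unseen patients = 4 + L·(1 − f)
- Error = planned triaged-only difference minus the all-registered difference

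**Worked example.** 5% v 1%, so the planned difference is 4.0 points; 2 leavers on control and 5 on intervention weekends.
- Nobody reaches the GPC: intervention 133.8 × 0.05/138.8 = 4.82%; control 136.8 × 0.01/138.8 = 0.99%; difference 3.8, so the plan is 0.2 points too high. Unseen patients are 6 v 9 (control v intervention), while the planned indicator shows 4 v 4.
- All intervention leavers and no control leavers reach it: (133.8 × 0.05 + 5)/138.8 = 8.42%; difference 7.4, so the plan is 3.4 points too low. Unseen patients are 6 v 4.

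**All corners.** Each cell gives the error for question 1 in points as intervention p runs from 5% to 20%, then unseen patients, control v intervention.

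| Leavers, control v intervention | None reach GPC | All reach GPC | Only intervention leavers do | Only control leavers do |
|---|---|---|---|---|
| 2 v 2 | +0.1 to +0.3; 6 v 6 | +0.1 to +0.3; 4 v 4 | −1.4 to −1.2; 6 v 4 | +1.5 to +1.7; 4 v 6 |
| 1 v 2 | +0.1 to +0.3; 5 v 6 | −0.7 to −0.4; 4 v 4 | −1.4 to −1.2; 5 v 4 | +0.8 to +1.0; 4 v 6 |
| 2 v 5 | +0.2 to +0.7; 6 v 9 | −2.0 to −1.5; 4 v 4 | −3.4 to −2.9; 6 v 4 | +1.6 to +2.1; 4 v 9 |
| 2 v 8 | +0.3 to +1.1; 6 v 12 | −4.0 to −3.2; 4 v 4 | −5.5 to −4.6; 6 v 4 | +1.7 to +2.6; 4 v 12 |

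If the 15 exclusions lie outside the 8000 (N = 153.8), no error changes by more than 0.6 points.

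**Reading the table.** With equal numbers of leavers and the same destinations in both arms, the error is at most 0.3 points. The smallest all-registered difference anywhere is 2.3 points (5% v 1%, 2 v 8, only control leavers reaching the GPC), which is still positive; that corner also runs against what one would expect from the information shown. For question 5 at 2 v 5, the ratio of unseen patients, intervention to control, runs from 4/6 = 0.67 to 9/4 = 2.25.

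**The case against.** The restriction is open and deliberate. Extended triage is the intervention, so analysing triaged patients is defensible, and the safety indicator is expressly a post-triage count. Triage is meant to take place ideally within ten minutes of arrival, so few may leave first. Nothing says that the leaflets prompt anyone to leave; hearing that a nurse will advise on where to go is as good a reason to wait. Every count above is assumed. A data management plan and a separate process protocol are mentioned, and either might count these patients.

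Most of this stands, and it limits the point to a minor one. It does not remove it. Stating an exclusion does not show that it is balanced, and ten minutes is an ideal rather than a limit. The sentence "The EDs own software allows us to calculate the number of excluded patients" shows that some counting is possible, but it concerns patients left out by the inclusion rule, not pre-triage leavers, and it does not mention weekend type.

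A reader might infer three stronger things. One is that the plan hides a rise in unseen patients on intervention weekends; no passage gives a reason to expect extra leavers to go home rather than to the GPC. Another is that question 1 is biased in a known direction; the sign depends on destinations that nobody has recorded. The third is that the rules on leaving contradict each other; the safety indicator is clearly post-triage, and the looser dropout sentence and the unqualified question 5 are differences of scope.

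**Conclusion.** The point holds as a minor gap in scope and reporting. The population in the analysis is narrower than the population the plan enters, the narrowing follows randomisation, and the plan could not show whether it is balanced between arms. Size and direction are unknown: there are no pre-triage counts, and the documents do not say whether the waiting-room information is seen before triage. If almost nobody leaves before triage, both effects are close to nil. The finding of an increase on question 1 is not threatened under the ranges tried; what could move is its size, and how completely question 5 is answered.

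**What to change.** In Recruitment strategy and expected dropout, replace the sentence that leaves these patients unanalysed with a rule to report, by weekend type, the numbers of registered eligible, left-before-triage and triaged patients from ED registrations. First confirm that the ED software can supply them.

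Keep the triaged-only analysis of question 1 and the post-triage safety indicator as planned, and say that the indicator covers only part of question 5. For both questions add one sensitivity analysis on all registered eligible patients, with bounds that assume none or all of the pre-triage leavers in each arm went to the GPC. This needs counts only. Describe the bounds as a limit, not a test.

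Linkage to GPC reports is optional. A registration without a report is not among the three report types that iCAREdata is said to link. If linkage proves possible, the time window should match the study period of a few hours. The whole opening from Friday 7 pm to Monday 6 am is 59 hours and could pick up a visit for another complaint.

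The cost is one extra registration extract, and bounds for question 5 that may be wide. Pre-triage leavers have no flowchart, urgency code or triage nurse, so they cannot enter questions 1.1, 1.3 or 2, or the nurse-nested model; those stay as they are.

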# Methodology for the medical aspect

The data necessary for this work package are part of a routine clinical report. We will use three types of these reports: triage-consultation reports, ED consultation reports and GPC consultation reports. We will collect these data using the iCAREdata database. This database can link our three types of clinical reports using an irreversibly coded national number. Due to data protection rules, the iCAREdata data manager will execute all queries and only aggregated results will be transferred to the researchers. For more complex statistical analysis, the data manager will transfer an analysis specific table or the analysis will be carried out on the computer of the data manager in cooperation between the researcher and the data-manager. A detailed data management plan is available. The correctness of a triage decision depends on the patient's situation:

- At the GPC (patients compliant to a GPC advice or non-compliant to an ED advice): the ratio of patients referred to an ED to the total number of patients coming from the ED of AZ Monica.
- At the ED (patients compliant to an ED advice or non-compliant to a GPC advice): the physician will answer the same question for all patients: "Should this patient better go to the GPC?". The correctness is defined as the ratio of the patients with a positive answer to this question to the total number of patients staying at the ED after triage.

The parameters of interest in questions 1 through 8 are (conditional) proportions, which calls for analysis by a non-linear model (e.g. binary logistic regression). The study design results in the creation of nested data, where patients are nested in weekends, and weekends are nested in (multiple) nurses. Appropriate analysis of such auto-correlated data requires a nonlinear mixed model. During the first months, data will be used to produce point-estimates of these proportions (e.g., patients seen by GP, correct triage decisions, all false positives, type 1 false positives, patients left without being seen, etc.). With increasing duration of the study, incoming data will be used to explain variability of these probabilities in terms of patient background characteristics, operating nurses/emergency physician, season, etc. Statistical assistance will be called for in order to conduct these analyses.

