#### *Research question:*

- 1. What is de the difference in the proportion of study patients seen by the GP between intervention and control weekends?
  - 1.1. Is this proportion associated with the patient's presentation (chosen eMTS flowchart and urgency)?
  - 1.2. Is this proportion associated with the occupancy rate of the ED and/or GPC?
  - 1.3. Is this proportion associated with the operating triage-nurses and/or the operating emergency physician?
  - 1.4. Is this proportion associated with the patient's background characteristics? (sex, age, community, insurance status)?
  - 1.5. Is there seasonal variation in this proportion?

Secondary hypothesis: a nurse using the eMTS is able to detect primary care patients. We can assess the correctness of the nurse's allocation advice as a diagnostic instrument.

The results of the triage consult is either a GPC or ED advice. Arbitrarily we will call a GPC advice a positive diagnosis. The gold standard is the opinion of the physician (either emergency physician or GP) after the consultation. This standard is used in almost all of the literature(3), as no better gold standard is available. We are aware of some disadvantages: this opinion depends on the personality and other characteristics of the treating physician and some patients have presentations suitable for both ED and GPC. On the other hand, agreement between nurse and physician is important for the feasibility of extended triage.

The way we will measure the correctness of the triage advice depends on whether the patient is compliant to this advice. This makes Table 1 more complex:

	Patient goes to GPC		Patient goes to ED	
Opinion physician	GPC correct	Had to go to ED	ED correct	Had to go to GPC
Advice GPC	Correct decision 1	False positive 1	False positive 2	Correct decision 2
Advice ED	False negative 1	Correct decision 3	Correct decision 4	False negative 2

Table 2: patient categories for the eMTS as a diagnostic instrument

Because our eMTS is risk adverse, we already know we will have a certain amount of false negative 2: patients who are compliant to the advice of ED although they had to go to the GPC according to the emergency physician. This category is not our primary focus.

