We are mostly interested in false positive 1: patients who complied with the advice GPC but should have stayed at the ED. Some of these patients might be subject to a safety risk. For example, a patient with a heart attack allocated to the GPC might lose valuable time. This category is the same as the proportion of study patients allocated to the GP but referred back to the ED. We will give this category special attention in our process analysis.

Finally, we are also interested in the category correct decision 2: patients who are not compliant to a correct GPC advice. These patients made an inefficient decision so there is room for improvement.

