#### *Research questions:*

- 2. What is the validity of the eMTS as a preliminary diagnostic instrument to detect a primary care patient?
  - 2.1. What is the proportion of correct extended triage decisions measured by comparing the triage advice with the urcenty evaluation of the physician?
  - 2.2. What is the proportion of correct extended triage decisions with advice GP measured by the proportion of referrals within this category?
  - 2.3. What is the proportion of patients wrongly assigned to GPC (all false positives)?
  - 2.4. What is the proportion of patients wrongly assigned to GPC who did go to the GPC (type 1 false positives)
- 3. What is the proportion of patients who are not compliant to a correct GPC advice (Correct decision 2).
  - 3.1. What are the determinants for this non-compliance? (same determinants as studied in question 1.1-1.4)
- 4. What is the proportion of patients in which the nurse gives another advice comparing to the eMTS?
- 5. Does the intervention influence the number of patients left without being seen?
- 6. What is the shift in workload during the different phases of this study for all participating healthcare providers (GPs, triage nurses and ED physicians)?
- 7. Does the epidemiology in terms of reasons for encounter and diagnoses at both OOH services differ between intervention and control weekends?
- 8. What is the proportion of patients who return to the ED within two weeks for each of the categories described in table 2?

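### The two correctness ratios in the medical methodology contradict Table 2: for patients who follow the advice, they count the errors and leave out the correct decisions

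*Combined protocol and SAP*

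**What the plan says.** Under Hypotheses and Research questions, Table 2 crosses the advice given, the place attended and the physician's opinion. It has eight cells: Correct decisions (CD) 1 to 4, False positives (FP) 1 and 2, and False negatives (FN) 1 and 2. A GPC advice is the positive result. The text adds that "The way we will measure the correctness of the triage advice depends on whether the patient is compliant to this advice". Research question (RQ) 2.1 follows the table: "What is the proportion of correct extended triage decisions measured by comparing the triage advice with the urcenty evaluation of the physician".

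Methodology for the medical aspect then gives one ratio per site.

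- **GPC:** for "patients compliant to a GPC advice or non-compliant to an ED advice", the measure is "the ratio of patients referred to an ED to the total number of patients coming from the ED of AZ Monica".
- **ED:** for patients who followed ED advice or declined GPC advice, the physician says whether the GPC would have suited the patient better. The definition follows: "The correctness is defined as the ratio of the patients with a positive answer to this question to the total number of patients staying", meaning everyone who remains in that department once triaged.

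Two statements fix how a referral and a yes should be read when the advice was followed. On FP1, the protocol says "This category is the same as the proportion of study patients allocated to the GP but referred back to the ED". On FN2 it says "Because our eMTS is risk adverse, we already know we will have a certain amount of false negative 2". Both categories are errors in Table 2.

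RQ 2.2 asks: "What is the proportion of correct extended triage decisions with advice GP measured by the proportion of referrals within this category".

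**The concern.** Correctness of the nurse's advice is the secondary hypothesis, and this methodology section is the only place in the protocol that writes it as site-specific ratios. Taken literally, the ED ratio credits the triage with patients wrongly kept at the ED and gives no credit for patients rightly kept there. The GPC ratio credits referrals back, which the protocol itself treats as the category of greatest safety interest. An analyst cannot apply these ratios and also apply Table 2. If the ratios were used for RQ 2.1, the reported correctness would be wrong and could move in the wrong direction as triage improves.

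**Working it through.** **1. Map the ratios onto Table 2.** This step needs no assumed figure. A referral to an ED is read as the GP's opinion that the patient belonged at the ED, as the protocol does for FP1.

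| Site | Numerator as written | Numerator by Table 2 | Denominator |
|---|---|---|---|
| GPC | FP1 + CD3 | CD1 + CD3 | CD1 + FP1 + FN1 + CD3 |
| ED | CD2 + FN2 | CD2 + CD4 | CD2 + FN2 + CD4 + FP2 |

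Among patients who followed the advice, the errors FP1 and FN2 are counted and the correct cells CD1 and CD4 are left out. Among those who did not, the correct cells CD3 and CD2 are counted. With full compliance, perfect triage scores 0% at both sites and wholly wrong triage scores 100%.

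**2. Test the complement.**

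- GPC: 1 minus the ratio is (CD1 + FN1)/denominator. It equals Table 2 correctness only if FN1 = CD3.
- ED: 1 minus the ratio is (CD4 + FP2)/denominator. It equals Table 2 correctness only if FP2 = CD2.

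Full compliance makes all four of these cells zero. Nothing else guarantees the equalities.

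**3. Direction.** Let s be the GPC-suitable share, se the share of suitable patients advised GPC, sp the share of the others advised ED, and cG and cE the compliance with GPC and ED advice. Assume compliance does not depend on true suitability within an advice group. Put k = cG + cE − 1.

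- At the GPC: suitable = s[(1 − cE) + se·k]; not suitable = (1 − s)[cG − sp·k].
- At the ED: suitable = s[cE − se·k]; not suitable = (1 − s)[(1 − cG) + sp·k].

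The written GPC ratio is the not-suitable share at the GPC. The written ED ratio is the suitable share at the ED. If k > 0, lowering se or sp with the other held fixed raises both ratios.

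**4. Illustration.** The documents give no compliance or case-mix figures and no correctness figure to reproduce, so every input is assumed: s = 0.30, cG = 0.70, cE = 0.98.

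*Perfect triage (se = sp = 1).* CD1 = 0.210, CD2 = 0.090, CD3 = 0.014, CD4 = 0.686; the other cells are 0.

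- GPC as written: 0.014/0.224 = 6.3%; complement 93.8%; Table 2 100%.
- ED as written: 0.090/0.776 = 11.6%; complement 88.4%; Table 2 100%.

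*Less accurate triage (se = 0.70, sp = 0.95).* CD1 = 0.1470, CD2 = 0.0630, CD3 = 0.0133, CD4 = 0.6517, FP1 = 0.0245, FP2 = 0.0105, FN1 = 0.0018, FN2 = 0.0882.

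- GPC as written: (0.0245 + 0.0133)/0.1866 = 20.3%; complement 79.7%; Table 2 (0.1470 + 0.0133)/0.1866 = 85.9%.
- ED as written: (0.0630 + 0.0882)/0.8134 = 18.6%; complement 81.4%; Table 2 (0.0630 + 0.6517)/0.8134 = 87.9%.
- RQ 2.2 read literally: 0.0245/(0.1470 + 0.0245) = 14.3%; its complement is 85.7%.

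*Range.* Over s = 20, 30, 40%, cG = 50, 70, 90% and cE = 95, 98, 99% (27 combinations), perfect triage scores 1.6–28.6% at the GPC and 2.5–26.0% at the ED. The less accurate triage scores higher than perfect triage at both sites in all 27.

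**5. Limit of the direction result.** With the same s, cG and cE, move from se = 0.70, sp = 0.95 to se = 0.40, sp = 0.99. Overall accuracy, s·se + (1 − s)·sp, falls from 0.210 + 0.665 = 87.5% to 0.120 + 0.693 = 81.3%. The written GPC ratio also falls, from 20.3% to (0.0049 + 0.01386)/0.10636 = 17.6%. When one accuracy is traded for the other, the GPC ratio need not rise as overall accuracy drops.

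**The case against.** The strongest defence is that the meaning is plain from context. Table 2 and the wording of RQ 2.1 are sound. Later in the same methodology section, correct triage decisions, all false positives and type 1 false positives are listed as proportions to estimate, which are Table 2 terms. The two bullets could be read as naming each site's source of information: referral at the GPC, the physician's answer at the ED. This stands as evidence of intent and makes a drafting slip likely. It does not remove the conflict, because the ED sentence is an explicit definition with a stated numerator.

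RQ 2.2 is a weaker case. Being measured by referrals can mean through their complement, and the text on FP1 makes the direction clear. That is a wording matter only.

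Three stronger readings are tempting and are not supported:

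- *Less accurate triage always scores higher.* This holds when se or sp falls with the other fixed, under the conditions in step 3. Step 5 shows that it can fail at the GPC under a trade-off, which is relevant to a deliberately risk-averse instrument.
- *The wrong ratios will be what is run.* The protocol refers to a separate detailed data management plan, which is not among the documents. The actual query definitions may be there.
- *The comparison of intervention and control weekends is compromised.* No part of RQ 2 asks for a between-arm comparison, and compliance has no ordinary meaning in control weekends, when the advice is not disclosed.

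**Conclusion.** The two ratios are wrong as written. The stated ED definition cannot be followed together with Table 2 and RQ 2.1, and the GPC ratio has the same reversal for patients who follow the advice. Because each ratio pools patients who followed the advice with those who did not, reading it as its complement does not in general repair it.

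The contradiction rests on the cell mapping alone. The percentages show only how far the two definitions could diverge: they depend on assumed case mix and compliance, and on compliance being independent of true suitability within each advice group.

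The effect is confined to the secondary question of whether the advice was correct: RQ 2.1 if it is computed from these ratios and, as a matter of wording, RQ 2.2. The primary outcome, RQ 2.3, RQ 2.4 and RQ 3 are unaffected. It should be corrected before the correctness results are produced.

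**What to change.** Replace the two ratios with definitions by advice group, using Table 2 cells:

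- **ED correctness** = (GPC advice with yes + ED advice with no) / patients seen at the ED after triage. If the denominator is restricted to patients with a recorded answer, say so, since the present text uses all who stay at the ED, and report the number unanswered.
- **GPC correctness** = (GPC advice not referred + ED advice referred) / patients seen at the GPC who came from the study ED.
- **RQ 2.1 overall** = (CD1 + CD2 + CD3 + CD4) / the sum of all eight Table 2 cells. State that RQ 2.1 uses this formula.
- **RQ 2.2** (minor wording): 1 minus the referral proportion among GPC-advised patients seen at the GPC.

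Check that any query definitions in the data management plan agree. The cost is wording and query logic only: the advice, the place attended, the referral and the physician's answer are already part of the planned data.

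### ED correctness is divided by everyone who stays at the ED, so an unanswered physician question counts as not-yes

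*Combined protocol and SAP*

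**What the plan says.** In section 4, Methodology for the medical aspect, the ED physician is asked "Should this patient better go to the GPC", and the plan intends that "the physician will answer the same question for all patients". This covers two groups of stayers: those who followed ED advice and those who declined GPC advice. The measure is then fixed in one sentence: "the ratio of the patients with a positive answer to this question to the total number of patients staying at the ED after triage", where a positive answer is a yes.

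The same section describes the source as routine reporting: "The data necessary for this work package are part of a routine clinical report". The database manager runs the queries and normally passes on aggregates only, with an exception for more complex analyses.

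Under Hypotheses and Research questions, the reference standard is an expressed judgement: "The gold standard is the opinion of the physician (either emergency physician or GP) after the consultation". Table 2 scores it separately by advice:

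- ED advice: yes is false negative 2, no is correct decision 4.
- GPC advice, patient stays at the ED: yes is correct decision 2, no is false positive 2.

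Table 1 has its own column for patients who leave unseen after triage, and Table 2 has none. Recruitment strategy and expected dropout calls them dropouts and puts them at fewer than five a weekend. The protocol gives no rule for an unanswered question.

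**The concern.** The numerator counts yes answers and the denominator counts people. A patient with no recorded answer stays in the denominator and cannot enter the numerator, so the ratio cannot tell a blank from an explicit no. Yet the reference standard is an opinion, and a blank is not one.

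Questions 2.1 (share of correct decisions) and 2.3 (all wrong assignments to the GPC) are at stake, because both use the ED physician's answer. The plan also wants to explain variation in these proportions by nurse, emergency physician and season. If completion differs across those factors, part of the apparent variation would be variation in form filling. If only aggregated ratios are passed on, the researchers would not see this unless blanks are counted separately.

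**Working it through.** The plan states no figure for this ratio, so there is nothing to reproduce. The check is direct algebra.

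**Inputs not in the documents (assumed):**

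- m, share of stayers with no answer: 5% to 30%
- p, true yes share under ED advice: 0.10 to 0.30, example 0.20
- q, true yes share under GPC advice among stayers: 0.60 to 0.80, example 0.70
- w, share of stayers with ED advice: 0.6 to 0.9, example 0.8
- blanks unrelated to the physician's opinion

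**Step 1: effect on the yes share.** With all stayers in the denominator, the observed yes share is the true share × (1 − m).

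**Step 2: scored by advice as in Table 2, with that denominator.**

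- ED advice correct = 1 − p(1 − m), a bias of +p × m.
- GPC advice correct = q(1 − m), a bias of −q × m.

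| m | ED advice (true 0.80) | GPC advice (true 0.70) |
|---|---|---|
| 0 | 0.80 | 0.70 |
| 5% | 0.81 | 0.665 |
| 10% | 0.82 | 0.63 |
| 20% | 0.84 | 0.56 |
| 30% | 0.86 | 0.49 |

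Over the assumed ranges of p and q at m = 10%, the bias is +1 to +3 points for ED advice and −6 to −8 points for GPC advice. At m = 20% it is +2 to +6 and −12 to −16 points. For question 2.3, false positive 2 among GPC-advised stayers reads 1 − 0.63 = 0.37 instead of 0.30 at m = 10%.

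**Step 3: both groups pooled, Table 2 scoring.** The net bias is m × (w × p − (1 − w) × q). At m = 10% and w = 0.8 this is 0.10 × (0.16 − 0.14) = +0.002, so 0.780 reads 0.782. The two errors largely cancel here, and the distortion shows mainly in the results by advice.

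**Step 4: the ratio as literally written.** Yes counts as correct for every stayer. At m = 10% it goes from 0.20 to 0.18 for ED advice, from 0.70 to 0.63 for GPC advice, and from 0.8 × 0.20 + 0.2 × 0.70 = 0.30 to 0.27 pooled. Blanks lower it in both groups. With no blanks it still gives 0.20 for ED advice where Table 2 gives 0.80, so a new denominator alone does not repair it.

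**Step 5: the one group with a documented size that cannot have an answer.** Included patients per weekend are about 8000/52 − 15 = 139. Fewer than five leave unseen after triage, so under 5/139 = 3.6% of included patients (somewhat more as a share of stayers). If all were counted as staying, the biases at m = 3.6% would be about +0.20 × 3.6 = +0.7 and −0.70 × 3.6 = −2.5 points.

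**Step 6: bounds at m = 10%.**

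- ED advice: explicit no = 0.80 × 0.90 = 0.72. Correctness lies between 0.72 (all blanks yes) and 0.82 (all blanks no).
- GPC advice: explicit yes = 0.63. Correctness lies between 0.63 (all blanks no) and 0.73 (all blanks yes).

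The all-stayers denominator with Table 2 scoring is therefore always the all-no bound. Dividing by answered patients gives 0.72/0.90 = 0.80 and 0.63/0.90 = 0.70.

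**The case against.** The strongest reply is that the plan intends an answer for every patient, so stayers and answered patients are meant to be the same set. On that reading the gap is an absent rule for blanks, not a choice of the wrong denominator. This stands as far as the size goes: with full completion nothing changes, and no completion rate is documented. It does not remove the point. An intention is not a rule, and the ratio as written has a definite effect on any blank that does occur.

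A reader might infer that the plan scores blanks as agreement with the ED and so flatters ED advice. The documents do not support that. The quoted ratio counts yes as correct whatever the advice, and under it blanks lower correctness in both groups. Table 2 alone has no cell for a blank. The pattern in Step 2 arises only when the Methodology denominator is combined with Table 2 scoring, and no section prescribes that combination.

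A reader might also infer that patients who leave unseen are scored as correctly at the ED. Table 1 gives them their own column, Table 2 omits them, and question 5 studies them. Only the wording of the denominator leaves their place open.

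Finally, the reach is limited. Type 1 false positives (question 2.4), the plan's main interest within the validity analysis, and question 2.2 rest on referral at the GPC and are unaffected. The plan also says that false negative 2 is not its primary focus. A data management plan and a staff manual are mentioned but are not part of these documents, and they may deal with completion. All of this stands, and it keeps the severity low.

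**Conclusion.** The point holds as a low-severity matter. The ED correctness ratio treats an unanswered question like a no, and the protocol has no rule for blanks. The bias is zero at full completion and otherwise unknown. Every magnitude above except the leavers' share rests on assumed values of m, p, q and w and on blanks unrelated to opinion. On those assumptions and Table 2 scoring, 10% blanks shift ED advice by about +2 points and GPC advice by about −7 points, while the pooled figure hardly moves. The larger shifts in the table need 20% to 30% blanks, for which the documents give no support. The results exposed are questions 2.1 and 2.3, mainly when read by advice.

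**What to change.** In Methodology for the medical aspect, replace the ED correctness sentence so that it:

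1. scores correctness separately by advice according to Table 2 (under ED advice an explicit no is correct; under GPC advice an explicit yes is correct);
2. uses as denominator the stayers for whom the physician recorded an explicit yes or no;
3. states that patients who left after triage without being seen are not counted as staying;
4. has the data manager count blanks separately and report completion by advice and weekend type;
5. gives bounds with all blanks set to yes and all set to no for questions 2.1 and 2.3.

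Items 1 and 2 belong together, since the denominator alone would leave a ratio that contradicts Table 2 for ED advice. The cost is a short rewrite of one definition and a few extra output lines. Denominators become slightly smaller. The estimate among answered patients is unbiased only if blanks are unrelated to the opinion, and the bounds show how far that assumption matters.
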